All hard copy data will be stored in locked filing cabinets in a secure office located on a secure corridor and will only be made accessible to the research team. The use of keys is restricted to those members of staff who require them and staff are required to sign for keys.

All electronic data will be stored on password protected systems in a secure office and will only be made accessible to the research team as necessary. Participants' personal details will be stored in separate locked filing cabinets (hard copies) or on secure, password protected, internal systems (electronic copies) in a secure locked office. The Inquiry's internal network cannot be accessed by external servers and therefore is only accessible by individuals registered to do so and their access is restricted. All computers are encrypted and password protected.

University staff are forbidden from transferring personal information from University computer systems, (e.g. email), to any other device that is not registered with the Centre, including CDs; floppy or hard disks; tablets; laptops; USB memory modules or any other storage media or device. Where data must be transferred onto a portable device, the device must be registered with the Centre and

must meet therefore must meet the associated requirements for password protection and encryption. The university use Truecrypt, an AES 256 encryption algorithm.

The information in the study will be bound by the Confidentiality Policy which forms part of the Information Security and Management policy. Confidentiality clauses are included within all staff contracts and staff are made aware of their responsibilities.

The research team will collect identifiable data (name, date of birth and prison number) but these data will not be used in the analysis or publication of findings. Identifiable data will be stored securely and separately from outcome data. A personal identifier (a three-digit number), will be used to link the identifiable and non-identifiable data. The identifier key will also be stored securely and separately from outcome data. Other personal data pertaining to participants' self-reported criminal justice history, mental and physical health, sensory or learning difficulties and use of substances and/or medication will also be collected. However, these data will only be published as overall sample descriptives, so no individual will be identifiable.

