Data from Part 1 will be used to produce detailed case vignettes describing several archetypical cases of varying levels of severity of cognitive impairment and these will be presented to a panel of experts. The panel will then design pathways of care for cognitive impairment of varying severity and will contribute to the development of a training pack for the identification of cognitive impairment for staff working in prison. Our health economist will estimate and aggregate the costs of these packages of care in relation to Part 1 prevalence data.

Start date: 01/07/2016 Duration: 36 months

2. Research Aims and Study Objectives

We will validate a standard assessment tool and develop both care pathways and staff training specific to the prison environment, which will improve the quality, accessibility and organisation of services for older prisoners. We aim to increase staff confidence in identifying and supporting older prisoners with cognitive impairment/dementia and to move towards equivalence of prison-based care with community provision.

In England and Wales:

1) Estimate prevalence of cognitive impairment including dementia amongst the older prisoner population;

2) Validate the Six Item Cognitive Impairment Test (6CIT; Brooke & Bullock, 1999) for prisoners aged 50+;

3) Identify service needs and appropriate care pathways for older prisoners with cognitive impairment throughout custody and on discharge to the community;

4) Establish prison and healthcare staff training needs for identifying, assessing and supporting cognitively impaired older prisoners; and

5) Develop an appropriate training support pack.

3. Background

Across the developed world, the number of older adults in prison is rising (Moll, 2013). In England and Wales, prisoners aged over 60 years are proportionally the fastest-growing age group, followed by those aged 50-60 (Ministry of Justice (MoJ), 2015). Between 2004 and 2014, the number of older male prisoners has more than doubled from 1,655 to 3,720 aged over 60 years and 5,268 to 11,980 over 50 years. At the same time, the number of women over 60 has increased almost fourfold, from 25 to 96, while those over 50 have also more than doubled, from 209 to 437 (MoJ, 2015). A similar pattern has been shown in other countries, including the US (West, Sabol & Greenman 2010), Australia (Grant, 1999), Japan (Yamaguchi, 2011), and Canada (Uzoaba, 1998). This trend is likely to continue (Prison Reform Trust, 2011).

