We will aim to recruit at least860 prisoners aged 50 and over, including 269 women and 591 men. Within each sex, this sample size will allow the estimation of a prevalence of 7% (based on Hayes et al., 2012) with 2% precision (95% confidence intervals (CIs) 5% to 9%, applying finite sample corrections for each sex).

Sampling Procedure

We have developed our sampling procedure based on a review of the existing literature.

The sample will be drawn randomly from all female prisons and a representative range of adult male prisons across England and Wales, including local prisons holding those on remand, serving short sentences and in the early part of long sentences; training and dispersal prisons holding men part-way

through long sentences; high secure establishments holding those considered to be high risk; and open prisons holding short term prisoners deemed low risk and those in the final stages of long sentences, who are preparing for community release.

We have selected sites based on the proportion of each prison type in the prison estate as a whole-1 of the 8 high secure sites; 3 of the 31 locals; 5 of 51 category B or C training and dispersal prisons and 1 of the 7 category D/open prisons (as defined by the justice.gov.uk prison index – accessed 9th May 2016). We will also include a prison that has a specific wing for older and disabled prisoners. This is one of only two prisons in the country with a dedicated wing for prisoners based on their age and health needs. However, other prisons do have a large number of older prisoners as a result of them housing vulnerable prisoners (i.e. prisoners who are considered at risk from other prisoners, often due to their age or the nature of their offence).

We estimate that we will need to initially approach approximately 415 females and 896 males to allow for 20% refusing to participate and a further 14% who may be unavailable on the day; unable to consent; or have already been interviewed for the study in a previous establishment. (These estimates are based on Hayes et al. 2012 study, in which researchers conducted a one-day census of all prisons in North-West England and interviewed all males aged 60+ resident in each establishment).

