We will establish the total number of prisoners aged 50+ in the recruiting prisons and use these figures to calculate a sampling fraction, which will inform the proportion of prisoners we will approach at each site. For example, if there are a total of 1500 males aged 50+ in the prisons we approach, we will sample 60% of older prisoners at each site(896/1500). We will also stratify our sample according to age, an important variable when investigating cognitive impairment, as prevalence doubles with every increase of five years (Jorm & Jolley, 1998). We will therefore aim for half of our overall sample (for males and females) to be aged 50-69 years and half to be aged 70+.

We will review the recruited sample at regular intervals, pausing recruitment briefly (initially after we have recruited one quarter of the sample) and reviewing the sampling strategy, to consider, for example, whether we need to recruit a greater proportion of a particular age group. The first phase of recruitment (after one quarter are recruited) will effectively act as a pilot for the remainder.

Inclusion/Exclusion criteria

Anticipated inclusion criteria:

- i) Aged 50 or over;
- ii) Resident in one of the participating prison establishments on the day of the census.

Anticipated exclusion criteria:

- i) Considered by prison or healthcare staff not safe to interview alone due to their current risk assessment;
- ii) Previous inclusion in the study;
- iii) Does not have a functional command of the English language.
- iv) Lacking the capacity to provide informed consent AND an appropriate Personal or Independent Consultee cannot be identified/contacted, is unwilling to be consulted or makes the decision to refuse consent.

Participants will only be included if they can speak and understand English to a sufficient level and researchers are satisfied that their English language ability will not adversely impact their test scores. There are significant language biases in some tests, which cannot be overcome by straightforward translation or use of an interpreter. Some tests are available in other language

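### The age target for women cannot be met: it needs about 135 women aged 70 or over, and the protocol counts only 96 women over 60 in all prisons

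*Protocol*

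**What the plan says.** Section 4, Stage One, sets the recruitment target at 860 prisoners aged 50 and over, "including 269 women and 591 men". The size is chosen within each sex to estimate a prevalence of 7% "with 2% precision (95% confidence intervals (CIs) 5% to 9%, applying finite sample corrections for each sex").

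Under Sampling Procedure:
- Women are drawn from all female prisons. Men are drawn from a selected range of sites, one of which has a wing for older and disabled prisoners.
- Allowing for 20% refusals and a further 14% lost for other reasons, "we will need to initially approach approximately 415 females and 896 males".
- A sampling fraction is worked out from the number aged 50 or over in the recruiting prisons. In a worked example with 1,500 men, "we will sample 60% of older prisoners at each site".
- The sample is also to be stratified by age. The team will "aim for half of our overall sample (for males and females) to be aged 50-69 years and half to be aged 70" or over.
- Recruitment pauses after one quarter of the sample, and the age balance may then be revisited.

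Under Recruitment, names are picked by random number from one numbered list of eligible prisoners per site.

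The Background gives the 2004 and 2014 prison counts. For women, "the number of women over 60 has increased almost fourfold, from 25 to 96". The 2014 count of women over 50 is 437, against 209 in 2004. For men, the rise is "from 1,655 to 3,720 aged over 60 years and 5,268 to 11,980 over 50 years".

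**The concern.** The age target and the population counts appear in the same document and do not fit together for women. The target calls for more women aged 70 or over than there are women over 60 in the country's prisons.

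The age mix matters here. The protocol itself says prevalence doubles with each five years of age, so the share aged 70 or over directly moves a crude prevalence percentage. Those percentages feed the national projections (Stage Three) and the budget impact analysis (Part Four, Stage Four). A target that cannot be reached leaves the expected number of older women unstated. It also leaves the team to settle the age mix during fieldwork instead of beforehand.

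**Working it through.** **Participation rate.** The stated losses are 20% + 14% = 34%, leaving 66%. This reproduces the protocol's approach number for men: 591 / 0.66 = 895.5, or 896. The worked fraction also reproduces: 896 / 1,500 = 59.7%, or 60%.

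**Women: what the target needs.** 269 / 2 = 134.5, about 135 recruited aged 70 or over.

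**Women: what is available.** The 96 women over 60 include every woman aged 70 or over, so 96 is a generous upper limit.
- If all 96 were 70 or over and every one took part, the shortfall is 134.5 - 96 = 38.5, about 39.
- At 66% participation: 96 x 0.66 = 63 recruits over 60, and fewer aged 70 or over.

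**Women: allowing for growth since 2014 (assumption).** The annual factor is (96 / 25)^(1/10) = 1.144.
- 2016: 96 x 1.144^2 = 126 women over 60, and 126 x 0.66 = 83 recruits.
- 2019, when the 36 months end: 96 x 1.144^5 = 188, and 188 x 0.66 = 124 recruits.

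Both fall below 135 even if every woman over 60 were 70 or over.

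**Women: if the split were held rigidly.** With at most 63 in the older half, the female sample would stop at 2 x 63 = 126. With N = 437 and p = 7%, the 95% half-width is 1.96 x sqrt[(0.07 x 0.93 / 126) x (437 - 126) / 436] = 0.038, or 3.8 points against the planned 2.

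**Men.** The target is 591 / 2 = 295.5, about 296 recruited, and 295.5 / 0.66 = 448 approached, aged 70 or over. The national share over 60 is 3,720 / 11,980 = 31%. Applied to the 1,500 men of the example, this gives 466 over 60. The target would need 448 / 466 = 96% of that number to be both 70 or over and approached. This assumes that the sites share the national age mix, which the protocol does not say.

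**One fraction, one list.** An equal-probability draw reproduces the age mix of the list. At national shares it would recruit 591 x 0.31 = about 184 men over 60. For women the share is 96 / 437 = 22%, giving 269 x 0.22 = about 59 over 60. Those aged 70 or over would be fewer in both sexes. Such a draw would not by itself deliver half aged 70 or over.

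**Pooled reading.** If the half applies to both sexes together, 860 / 2 = 430 aged 70 or over are needed. Women supply at most 63, leaving 367 men, which is 367 / 591 = 62% of the male sample, or 367 / 0.66 = 556 to approach. At the national share the example holds 466 men over 60.

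**The case against.** The strongest reply is that the age split is only an aim, to be revisited after the first quarter of recruitment. The sample sizes and 2% precision are set by sex and do not depend on the split. The age-specific estimates in Stage Three are conditional on sufficient power. All of this stands, and it limits the harm of missing the target. It does not make the target reachable: a review can redirect effort but cannot add older women to the prison population, and no further female prisons exist to recruit.

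A reader might infer more than the documents support.
- **That the age target contradicts the 60% fraction.** The 60% is a worked example for men only, and the next sentence adds age stratification. A site fraction and different age fractions within a site can coexist. The protocol simply does not state the age fractions.
- **That the target is impossible for men.** The protocol gives no count of men aged 70 or over and no age mix for the chosen sites. One site has an older-prisoner wing, and the protocol notes that other prisons hold many older men. The national share is therefore not a ceiling for these sites.
- **That the female sample is effectively a census.** Setting 415 against 437 compares planned approaches with a 2014 count. The growth allowed for women over 60 would have to be allowed for all women over 50 too.
- **That 415 is an error because 269 / 0.66 = 408.** The figure is given as approximate, the gap is under 2%, and it has no bearing on the age target.
- **That selection would become uncontrolled.** Shortfalls are to be filled by drawing further random numbers, so this is not shown.

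**Conclusion.** On the protocol's own figures, the target of half the women aged 70 or over cannot be met. It needs about 135. At planned participation the upper limit is about 63 on the 2014 count, or about 83 with growth carried to 2016. Both limits are generous, because they treat every woman over 60 as 70 or over. On the 2014 count the conclusion needs no participation assumption, since 96 is already below 135. The 2016 and 2019 figures rest on the 2004-2014 growth rate continuing and on 66% participation.

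For men the target is doubtful only: it looks very demanding at the national age mix, but the site age mix is unknown. Reading the target as pooled across the sexes moves the burden to men and makes it harder for them, again subject to the site mix. The selection procedure as described would not by itself produce half aged 70 or over in either sex, so age-specific fractions are needed if older prisoners are to be over-represented.

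**What to change.** Amend Sampling Procedure and Recruitment before recruitment starts, and reconcile them with the counts in the Background.

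- **Women:** replace the half-and-half target with inviting all women aged 70 or over, or all women aged 50 or over, and state the number aged 70 or over expected from current prison counts.
- **Men:** set the target for 70 or over from the actual counts at the participating sites, and state separate sampling fractions for 50-69 and for 70 or over. The protocol already plans to establish the number aged 50 or over in the recruiting prisons. Splitting that count at 70 supplies what is needed.
- **Analysis:** wherever the fractions differ by age, weight the overall prevalence estimates back to the prison age distribution. If all women aged 50 or over are invited, their selection fractions do not differ by age.

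The cost is some rewording and one recalculation from counts that are to be collected anyway. The downside is that fewer women aged 70 or over will be expected than the protocol now implies, so their age-specific intervals will be wider. Weighted overall intervals will also be slightly wider than unweighted ones.

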A research nurse or other appropriate staff member within each of the prisons will act as a single point of contact (SPOC) for the research team. (This may be a different role across study sites (such as a Clinical Studies Officer (CSO), researcher or research facilitator, but we will ensure the individual is not in a directly caring role for prisoners, to avoid the potential for coercion during recruitment). The research team will provide the SPOC at each site with a census date and the SPOC will then identify potential participants who fulfil the inclusion criteria. They will do this by running a search on all prisoners in their establishment on the prison computer system (C-NOMIS) or healthcare system (Systmone). Once a numbered list of all potential participants has been generated, the SPOC will inform researchers of the number of eligible older prisoners they have identified. A member of the university-based research team will then use a random number generator to identify the numbers of those randomly selected for potential participation and will communicate these to the SPOC e.g. numbers 1, 3, 6, 7, 9....on this list. The SPOC will then conduct checks using the internal prison data systems to ensure that the individual meets the inclusion criteria and it is appropriate for them to be seen by the research team. For example, are they currently mentally and physically well enough to be seen; are they considered safe to be seen? It is inappropriate to use Criminal Justice staff, including prison health care staff, to make the first approach because of the potentially coercive (or perceived coercive) nature of the relationship in the prison environment

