The SPOC will then send an information and appointment slip to each of the individuals who have been randomly selected and are both eligible and appropriate to be seen. The slip will very briefly outline the study and will invite each individual to a one-to-one interview with a researcher. The slip will explicitly state that by attending their designated appointment, individuals will be meeting with a member of the research team to further discuss the potential for participation. Details of who to approach for further information or advice regarding the study, within the prison and prior to the appointment time, will also be included. (Interviews may be held in healthcare clinic rooms, in visits or in wing interview rooms, depending on the availability of rooms, procedures and governor preferences within each prison). This procedure is being followed in a current study which the PI is involved with and is more realistic and feasible than having someone within the prison going to see each potential participant and asking for their consent to pass details on to the research team. There may be in excess of 100 potential participants at some establishments and given the impact of austerity measures across the prison estate, requiring a member of staff to do this amount of work on our behalf would be a major barrier to completing the project. It would also be unfair to potential participants if this process was rushed or not done properly.

At their appointment time, potential participants who choose to attend will meet a researcher, who will provide them with initially verbal and then, if willing, written information about the study and an opportunity for further discussion. During the briefing process, participants will be made aware that if they choose to take part in the study, their data will be made available to other researchers, but that this will be in an anonymised format.

Following the procedure for obtaining consent as outlined below, if an individual consents to taking part, the researcher will conduct an initial interview, which will include the collection of demographic data and completion of the 6CIT and MoCA.

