Researchers will obtain the prison ID number of all who attend an appointment, regardless of whether they agree to participate in the study. This list will then be passed to the SPOC, who will match it against the list of those invited to appointments to identify anyone who failed to attend. If any individuals identified in the initial random sample fail to attend, the SPOC will attempt to make contact with them and ensure that the reason for their failure to attend was not related to an inability to comprehend the written information provided or to attend the appointment. This is an important step in ensuring that the sample is not biased by the indirect exclusion of those with a cognitive impairment. The SPOC will take great care to avoid coercing individuals into taking part or making individuals feel they have to account for their decision not to attend. Instead they will make it clear that the purpose is to check whether any individuals wanted to attend but were unable to, in which case, appropriate arrangements and additional support will be put in place to facilitate a meeting with the research team.

If the initial, randomly-selected sample from each site falls short of our recruitment target, researchers will randomly generate further numbers for the SPOC to check against eligibility criteria and invite to a meeting with researchers, until the target is reached.

Consent

The researcher will explain the project to the potential participant and will give them the information sheet as well as explaining their ethical rights (included in the appendices). The researcher will read and explain the information in these documents to the potential participant, showing sensitivity to the high levels of learning difficulties in this population and potential cognitive impairment.

At the beginning of the appointment the researcher will go through the information sheet and answer any questions that the prisoner wishes to ask. The researcher will explain what participation involves and how much time participation will take. They will also explain that participation is voluntary, that the prisoner is free to withdraw at any point and that their decision to participate, or not, will have no adverse effect on the care they receive or their other legal rights. The researcher will also discuss the arrangements to ensure confidentiality (and limits of this) and data protection. Limits to confidentiality would include information pertaining to:

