All potential participants will be provided with an information sheet outlining what participation in the study will involve and how data will be used. The study information sheets have been reviewed by ex-older prisoners via the RESTORE support network and by service users diagnosed with cognitive impairment at a local memory clinic for older adults. All participants will be required to give their formal, informed consent before any data is collected. Participants will be given sufficient time to consider the information provided and ask questions, prior to providing consent. All researchers will have had practise and training in obtaining informed consent.

ii. Prisoner participants lacking capacity

Given the nature of the main research question, it is important that we do not exclude individuals who lack the capacity to provide informed consent due to cognitive impairment or dementia. In line with the requirements of the Mental Capacity Act, Section 31(2005), there are reasonable grounds for believing that research of comparable effectiveness could not be carried out if the sample was confined to adults with capacity and there is clear potential to benefit both participants and individuals in the future with the same/similar impairing condition.

Where researchers have concerns that an individual lacks the capacity to provide informed consent, they will follow the steps of the process consent method (Dewing, 2007) and will proceed in line with the MCA (2005), as outlined previously.

c. Identification of Cognitive Impairment/Dementia

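### After the random draw, the site contact may withhold an invitation from people judged not well enough; this is not a listed exclusion, and those dropped are neither re-approached nor recorded by reason

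*Protocol*

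**What the plan says.** Section 4.a.ii (Recruitment) sets the order of events. The site contact lists potential participants, and the university team draws random numbers from that list. Then "The SPOC will then conduct checks using the internal prison data systems to ensure that the individual meets the inclusion criteria" and that "it is appropriate for them to be seen by the research team". The examples given for the second test are "are they currently mentally and physically well enough to be seen; are they considered safe to be seen". Appointment slips go only to "individuals who have been randomly selected and are both eligible and appropriate to be seen", so being appropriate to see is a condition on top of eligibility.

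Section 4.a.i lists four anticipated exclusions:

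- "Considered by prison or healthcare staff not safe to interview alone due to their current risk assessment"
- previous inclusion in the study
- no functional command of English
- "Lacking the capacity to provide informed consent AND an appropriate Personal or Independent Consultee cannot be identified/contacted", or the consultee is unwilling or refuses

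None concerns being mentally or physically unwell.

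Two other statements bear on this. In section 4.a.ii, the follow-up of people who miss their appointment is described as important for "ensuring that the sample is not biased by the indirect exclusion of those with a cognitive impairment". Section 10.b.ii says "it is important that we do not exclude individuals who lack the capacity to provide informed consent due to cognitive impairment or dementia".

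**The concern.** The gate sits between the random draw and the invitation. It has no threshold and is introduced only by example, and section 4.a.ii allows the procedure to vary by site. A judgement that someone is not mentally well enough can overlap with the condition whose prevalence is being estimated. If it does, the invited group is no longer a random sample of eligible prisoners with respect to the outcome, and drawing more numbers does not repair that.

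At stake is the Part 1 prevalence estimate, which feeds the projections in section 4.c and the budget impact analysis in section 7.d. The severe end of the range also matters for the mild, moderate and severe grouping used to select Part 3 cases and build the Part 4 vignettes.

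**Working it through.** **1. Does any listed exclusion cover the check?** The safety question corresponds to the first exclusion. The wellness question corresponds to none. Lack of capacity excludes only when the consultee route also fails, so it cannot stand in for wellness.

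**2. Do the protocol's safeguards reach the people dropped?**

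- *Non-attendance check (4.a.ii).* Attendees are matched against the list of those invited. The text then speaks of members of the initial random sample who fail to attend, but a person given no appointment cannot fail to attend one.
- *Consultee and process-consent route (4.a.ii, Individuals Lacking Capacity; 10.b.ii).* Researchers assess capacity at the appointment. Someone not invited never gets there.
- *Replacement (4.a.ii).* Further random numbers are drawn until the target is met. This restores the sample size but not the people lost.
- *Recording.* The team issues the random numbers and the site contact holds the invitation list, so drawn minus invited can be derived. The protocol does not ask for that count, or for ages or reasons.

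**3. Does the planned allowance for losses cover it?** Section 4.a.i allows 20% for refusal and 14% for people unavailable, unable to consent or already interviewed, which is 34% together. The men's approach figure follows: 591 / (1 − 0.34) = 895.5, stated as 896. For women, 269 / 0.66 = 407.6 against 415 stated, slightly generous. Unwellness is not named in the 14%, and an allowance of this kind protects numbers, not representativeness.

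**4. How large could the bias be?** Inputs:

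- true prevalence 7%, the planning value in section 4.a.i, taken here as the truth
- planned precision of 2 points (5% to 9%), same section
- f, the share of those drawn who are dropped: not in the documents, assumed
- R, how many times as common impairment is among those dropped as among the rest: not in the documents, assumed

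If p is the prevalence among those retained, the true value is (1 − f)p + fRp. Hence p = 0.07 / (1 + f(R − 1)).

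| f | R = 1 | R = 3 | R = 5 |
|---|---|---|---|
| 2% | 7.0% | 0.07/1.04 = 6.7% | 0.07/1.08 = 6.5% |
| 5% | 7.0% | 0.07/1.10 = 6.4% | 0.07/1.20 = 5.8% |
| 10% | 7.0% | 0.07/1.20 = 5.8% | 0.07/1.40 = 5.0% |

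The bias equals the full 2-point precision when f = (0.07/0.05 − 1)/(R − 1) = 0.4/(R − 1). That is 10% dropped at R = 5, or 20% dropped at R = 3.

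**The case against.** The check is a reasonable welfare safeguard. Section 9 says researchers will be guided by clinical staff on whether data collection and participant selection are appropriate. The wording is about current fitness and names neither cognition nor dementia. The exclusions are headed as anticipated, so the list may not be final. The two statements of intent are also narrower than they look: one concerns invited people who could not understand the slip or attend, the other people who lack capacity. Neither promises to see people who are acutely unwell.

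Much of this stands. It justifies not interviewing an unwell person, and it means the conflict is with the purpose of those statements more than with their letter. It does not remove the bias if fitness and impairment are related. The word for current fitness hints at deferral, but no re-check is described.

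Three stronger readings are tempting, and the documents do not support them:

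- *That those dropped are known to be likely cases.* This is an inference; no rate is given.
- *That the loss cannot be detected.* The total can be derived from the team's own draw. What is missing is a request for it and for the reasons.
- *That the estimate would fall below the planned 5% to 9%.* If 5% were dropped and half of them were impaired, the estimate would be (0.07 − 0.05 × 0.5)/0.95 = 4.7%. That assumes impairment more than ten times as common among those dropped (0.50/0.047) and 36% of all cases removed (0.025/0.07). Nothing in the protocol supports so extreme a contrast.

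The effect on the case studies is partly offset. Section 6.a lets healthcare managers refer Part 3 cases if Part 1 yields too few, and section 7.a also draws on literature and consultation. Neither helps the prevalence estimate or the costing built on it.

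**Conclusion.** The point holds as an unreconciled filter of unknown size. The protocol applies a wellness condition after random selection that its exclusion criteria do not contain, and neither the non-attendance check nor the consultee route reaches the people affected. Any bias is downward if impairment is commoner among those dropped, and nil if it is not.

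Under the assumed ratios of 3 to 5, the estimate moves from 7% to between 6.7% and 6.5% with 2% dropped, and to between 5.8% and 5.0% with 10% dropped. Only the last of these uses up the planned precision. The effect may be small, but an analysis plan could not correct it later if sites have not recorded who was left out and why. It is worth correcting because the correction is cheap, not because the study fails without it.

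**What to change.** 1. Reconcile section 4.a.i (exclusions), section 4.a.ii (post-draw check and non-attendance follow-up) and section 10.b.ii, so that the status of the wellness check is stated once.
2. Treat a finding that someone is not currently well enough as a deferral. The site contact checks again before data collection at that site closes.
3. Count anyone still not seen as an eligible non-participant, even if further numbers are drawn to reach the target.
4. Have the site contact return aggregate counts, by reason, age band and sex, of everyone drawn but not invited. Review them at the planned pause after one quarter of recruitment.
5. Report these counts with the prevalence estimate, together with a simple sensitivity range: the estimate multiplied by 1 + f(R − 1), with f taken from the log and R over a stated range such as 1 to 5.

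The cost is a short log form, a few protocol sentences and a little more site-contact time. The last matters because section 4.a.ii already treats staff workload as a barrier, so the form should hold counts only. Nobody unwell is interviewed, and no health record of a person who was never approached goes to the research team.
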